Analyses similar to those conducted for the NEST (primary outcome analyses) above will be performed for the secondary family caregiver hypotheses involving PHQ-9, GAD-7, and PTSS scores at T3 and T4. While family caregivers will be interviewed at T4 regardless of patient survival, patient death could complicate the analyses in two key ways: (1) Presence of missing data due to family loss to follow up (i.e., non-random missing data) and (2) differences in family caregiver distress by patient survival status (i.e., heterogeneous effect). 35 To address the impact of patient death on outcomes, after first exploring reasons for and predictors of dropout, we will conduct a 2-step supplemental analysis. In Step 1, missing T4 data due to loss to follow up among family caregivers of survivors will be multiply imputed via SAS PROC MI. In Step 2, we will account for T4 outcomes that are missing due to death via composite endpoint and principal stratification methods to estimate the causal effects of the intervention in the presence of these unidentified outcomes and complicated missing data patterns. 36,37 For the key patient outcome, receipt of goal concordant care, we will use logistic regression models adjusting for the stratification variables, to examine if rates at T3 differ by treatment group. The key healthcare systems outcome, post-randomization hospital length of stay (LOS), provides a unique challenge due to the high expected mortality rate (40-50%). In addition to descriptive analyses, steps to examine treatment group LOS differences will include: (1) a proportional hazards model with death treated as a censoring event; (2) a chi-square test of mortality rate differences; and (3) a Brunner-Manzel rank test for the composite death-LOS outcome. This last step implements a recently developed methodology of a composite outcome that incorporates a numerical value for death (i.e., coded as the worst possible outcome or the longest possible stay) in the observed LOS distribution. 38,39

Aim 3

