This randomized clinical trial will compare PCplanner to a usual care control condition. The PCplanner intervention may reduce unmet needs and psychological distress, increase goal concordance, and reduce length of stay. Therefore, this intervention could hold great promise for helping many others in similar situations in the future. However, this is not certain. In fact, subjects in the usual care control condition may experience similar or even greater benefits to those described for PCplanner. Then again, they may receive no particular benefit. Nonetheless, study involvement puts subjects at low risk for any adverse physical or psychological risk. Therefore, the potential benefits for participation justify the minimal risk to those enrolled in the proposed study. Financial compensation will not be emphasized as a benefit of participation in research.

11. Adverse Events (AEs), Serious Adverse Events, (SAEs), Protocol Deviations (PDs) and Unanticipated Problems (UPs).

As noted above, this is considered a minimal risk study. Since the project intends to enroll critically ill patients who are elderly, and therefore, at risk of multiple and significant comorbidities, hospitalizations, and even death, adverse and serious adverse events will be limited to events that directly affect the overall well-being and safety of the family member (research subject). Additionally, given that this is a self-directed, survey based study, it is anticipated that compliance of research subjects (family member or clinician) will be less than 100% and/or completed within the protocol window. As such, events related to incomplete or missed study procedures will not be considered a protocol deviation and therefore will not be reported to the institutional or

Protocol Version: 5.1 Dated: 13 June 2022 Page 19 of 42

sponsor officials. Rather, events occurring outside of the study protocol will be documented and recorded by the study team in the web application, EDC, and/or study source documents as applicable.

All participants will have access to the principal investigator's contact information 24 hours a day (shown in the consent form). If a telephone interview is required, it will be conducted by a trained study team member who has been trained to be sensitive to the nature of these issues.

Adverse Events (AEs) and Serious Adverse Events (SAEs)

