As noted above, the DSMB will have the power to stop the trial at their discretion. The following is a possible stopping plan that could be adapted by the study DSMB for inclusion in the final DSMB Charter. Because this is an early phase trial, we will not have formal stopping rules based on efficacy or futility. Criteria for intervention discontinuation and stopping based on safety concerns will be determined in partnership with the study DSMB and codified in the DSMB charter before enrollment begins. We propose a strategy similar to that included in our past ICU-based RCTs that included family caregivers (e.g., R01 HL109823, PI: Cox). Three-month all-cause mortality will be the primary adverse event for the patients in study. We will examine the distribution of deaths by treatment arm three times during the trial: at 15, 25, and 50 deaths. At each of these interim looks, we will examine the distribution of deaths by study group and conducted either a non-parametric sign test or Wilcoxon signed-rank test to test the difference in median number of deaths between the arms. We will use Haybittle-Peto guidelines and stringently set the p-value at 0.001 to flag a significant difference between arms at each of these interim looks. If this difference is observed, this would then indicate a closer examination of related constructs, as well as proximate causes and circumstances surrounding death (e.g., timing and location of death, withdrawal of life support or not, comorbidities and illness severity, clinician expectations of survival). We will use the Patient-Centeredness of Care Scale to provide additional information on the alignment of patient treatment and values at the time of death. Although past end of life interventions have not increased mortality, it is possible that by better focusing decision makers' attention on patients' values, higher mortality could be observed in the intervention group by identifying patients for whom prolonged life support would be a state worse than death (Patrick DL, et al. Ann Int Med. 139:410-415, 2003; Holloway RG, et al. JAMA. 298:802-804, 2007). Yet if PCplanner—a non-directive intervention—led to more decisions to forego life support, this would be ethically permissible if the treatments received reflected patient-centered care as assessed by the PCCS (Institute of Medicine, 2001; Lin GA, et al. Arch Intern Med. 169:1551-1553, 2009; Holloway RG, et al. 2007). The primary adverse event for family caregivers will be symptoms of psychological distress as measured by the PHQ-9 and PTSS at T2 and T3. We propose to examine the distribution of scores by treatment arm three times during the trial: at 25, 75, and 100 caregivers. Using methods similar to those above, we could examine circumstances more closely as per DSMB guidelines.

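### The first length-of-stay analysis censors death, gives a cause-specific discharge hazard rather than an effect on stay, and no step is named as deciding

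*Combined protocol and SAP*

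**What the plan says.** Section 8, Aim 2, calls LOS the key healthcare systems outcome and says that expected mortality of 40-50% makes it hard to analyse. Besides descriptive analyses it lists three steps:

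1. "a proportional hazards model with death treated as a censoring event"
2. "a chi-square test of mortality rate differences"
3. "a Brunner-Manzel rank test for the composite death-LOS outcome", in which death is "coded as the worst possible outcome or the longest possible stay".

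The section does not say which step decides the LOS conclusion, how discordant results are to be read, or what quantity step 1 estimates. It does not name the event in step 1. With death censored, leaving hospital alive is the only event left.

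Section 10 gives the hoped-for direction: "The PCplanner intervention may reduce unmet needs and psychological distress, increase goal concordance, and reduce length of stay". In section 12, the proposed stopping plan allows that "higher mortality could be observed in the intervention group by identifying patients for whom prolonged life support would be a state worse than death", while noting that past end-of-life interventions have not raised mortality.

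**The concern.** A patient who dies can no longer be discharged alive. Censoring at death removes that patient from the discharge risk set, as if later discharge had been possible at the rate of those still in hospital. The resulting HR is a legitimate cause-specific hazard ratio, but it is easily read as an effect on length of stay. Two misreadings matter.

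- If deaths come sooner in one arm among patients who were not going to be discharged, the risk set shrinks faster there. The HR then moves above 1 although no survivor left earlier.
- If the death hazard rises and the discharge hazard does not change, the HR stays at 1.00 although fewer patients leave alive.

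The first would appear as the benefit that the trial hopes to show. The second would hide a loss. Step 2 compares how many died, so it cannot see a change in timing.

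**Working it through.** **Plan's own figures.** The plan gives no power, event count or HR for LOS, so there is no LOS figure to reproduce. The sample size comes from NEST and does reproduce. The change SD is 21.1 × √(2(1 − 0.64)) = 17.90, and n = 2 × (1.96 + 0.84)² × 17.90² / 8.80² ≈ 65 per arm. That becomes 75 per arm randomized, the size used below.

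**Inputs.** From the plan: 75 per arm and mortality of 40-50%. Assumed, because the plan gives none: the distributions of stay and of time to death, and a 90-day horizon.

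**Why timing matters.** The cause-specific discharge hazard at time t is

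h(t) = (rate of live discharge at t) / (proportion still alive in hospital at t).

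Hold the numerator fixed (same mortality, same survivor stays) and move deaths earlier. The denominator falls, so h(t) rises.

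*Example at day 10, 45% mortality.* Survivor stay is gamma with shape 2 and mean 14 days. Death time is gamma with shape 2, mean 12 days in control and 6 days in the other arm. For shape 2 and scale s, the proportion remaining at t is e^(−t/s)(1 + t/s).

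- Survivors still in hospital: e^(−10/7)(1 + 10/7) = 0.582
- Patients who will die, still alive, control (s = 6): 0.504
- Patients who will die, still alive, other arm (s = 3): 0.155
- Risk set, control: 0.55 × 0.582 + 0.45 × 0.504 = 0.547
- Risk set, other arm: 0.55 × 0.582 + 0.45 × 0.155 = 0.390
- Hazard ratio at day 10: 0.547 / 0.390 = 1.40, with identical survivor stays

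**Case B, whole trial.** Same set-up: the patients who die would not otherwise have been discharged. There were 2,000 simulated trials per row, with HRs from 200,000 per arm. A false shorter stay means a significant result at two-sided 5% with HR above 1 (nominal 2.5%).

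| Mortality | Mean death time, control vs other arm (days) | HR, death censored | False shorter stay | Step 3 rejects | Subdistribution HR |
|---|---|---|---|---|---|
| 40% | 12 vs 9 | 1.14 | 9.0% | 4.9% | 1.00 |
| 45% | 12 vs 9 | 1.17 | 9.9% | 4.9% | 1.00 |
| 50% | 12 vs 9 | 1.19 | 10.4% | 5.5% | 0.99 |
| 40% | 12 vs 6 | 1.31 | 24.1% | 5.3% | 1.01 |
| 45% | 12 vs 6 | 1.37 | 27.9% | 5.1% | 1.00 |
| 50% | 12 vs 6 | 1.43 | 32.0% | 5.1% | 1.00 |

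Step 2 rejects in 5-6% of trials throughout.

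**Other distributions.** With survivors' median stay of 12 days and median death time of 10 days, halving death times gives HRs of 1.21, 1.31 and 1.43 at 30%, 40% and 50% mortality. Cutting them by a quarter gives 1.10-1.18. Across the set-ups tried at 30-50% mortality, a false shorter stay occurs in 7-33% of trials. At 20% in-hospital mortality with death times halved, the HR is 1.11.

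**Case A, independent times.** Take a discharge hazard of 0.055 per day and a death hazard of 0.045 per day, the latter raised 1.5-fold to 0.0675 in one arm.

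- HR for discharge: 0.055 / 0.055 = 1.00 (simulated 1.00, rejection 4.8%)
- Share leaving alive: 0.055 / 0.100 = 55% against 0.055 / 0.1225 = 45%
- Subdistribution HR: 0.79 (simulated)

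Making deaths earlier under independence (median 6.9 to 2.6 days, mortality 45.0% and 42.3%) also leaves the HR at 1.00.

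**Case C, shared frailty.** Sicker patients die sooner and leave later. Raising the death hazard 1.5-fold or 2-fold gives HRs of 1.06 and 1.12, with a false shorter stay in 4.9% and 6.8% of trials.

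**The case against.** The strongest reply is that the plan already sees the problem. The same sentence that censors death goes on to a composite that does not, and this composite rejects at about its nominal 5% when only the timing of death differs. That stands. It would be wrong to say that the plan's LOS analysis ignores death.

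Second, a death-censored Cox model is a valid estimator of the cause-specific discharge hazard. A reader might infer that earlier deaths must always look like a shorter stay. They need not: case A gives 1.00, and the artefact needs dependence between dying and readiness for discharge. Case B is the strong form of that dependence, and under shared frailty the shift is smaller. Such dependence is plausible in intensive care, but the documents do not quantify it.

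Third, section 12 speaks of higher mortality in the intervention arm, not of equal mortality with earlier deaths. It supports the concern that censoring could differ by arm, but not the specific scenario in case B. Fourth, the 40-50% is not stated to be in-hospital mortality, so the share censored during the stay may be lower. Fifth, no Kaplan-Meier discharge curve is planned, so the known overstatement from such a curve is not a fault of this plan.

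Finally, replacing step 1 outright with a Fine-Gray model is debatable. In case A it gives 0.79 although the discharge hazard is identical, because it mixes mortality into the answer.

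None of this answers the remaining gap. The composite is listed third with no priority, so a significant step 1 could be reported as a shorter stay when step 3 shows none.

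**Conclusion.** The point holds in limited form. Step 1 does not estimate an effect on length of stay, and the plan does not prevent it from being read as one. Where the patients who die sooner are those unlikely to be discharged, with mortality and survivor stays unchanged, the HR is about 1.1-1.2 for death times cut by a quarter and 1.2-1.4 for death times halved. A shorter stay is then falsely declared in 7-33% of trials against a nominal 2.5%. These figures rest on 75 per arm, 30-50% in-hospital mortality and assumed distributions. With independent times the HR is 1.00. In the reverse case, a higher death hazard at an unchanged discharge hazard also gives 1.00, while live discharge falls from 55% to 45% in the example.

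The documents do not support the stronger conclusion that the LOS plan as a whole is invalid, since step 3 is sound against the timing of death. LOS is secondary and has no power calculation of its own, so the NEST analysis and the sample size are untouched. The change is worth making before unblinded data are seen.

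**What to change.** In section 8, Aim 2, the LOS text should:

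- name the composite rank test (step 3) as the main LOS analysis and say that it decides when the steps disagree;
- add Aalen-Johansen cumulative incidence curves of live discharge and of death by arm, with a subdistribution HR as an option;
- keep the step 1 Cox model only if it is labelled a cause-specific hazard of live discharge, reported beside the cause-specific Cox model for death, and not read on its own as an effect on stay;
- name live discharge as the event in step 1, and state whether the 40-50% refers to in-hospital or 3-month mortality.

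The cost is a paragraph of wording, a few lines of SAS and slightly longer reporting. No new data are needed.

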- (3) Participants will be told that they can discontinue an interview or telephone session at any time and that they are also free to reschedule an interview or treatment session at any time within the week.
- (4) There is also a potential risk for identifying underlying mental health issues through the survey responses. For issues such as passive suicidal ideation or symptoms of depression, anxiety, or PTSD, an informational sheet will be provided with contact numbers for additional mental health services.
- (5) As a safety measure, used in past and current ICU-based clinical research, the study team will monitor participants closely beyond just the parameters of questionnaire scores. The study staff will monitor participants closely during any interviews performed and will refer those with any concerning level of emotional distress and/or relationship distress to the PIs to evaluate by phone or in person. This will be done immediately, particularly if there is staff concern about a participant who indicates suicidality.

All study participants will be informed of the suicidality response plan prior to signing the informed consent for their participation in the study. The PI or study team delegate(s) will complete the online Columbia Suicide Severity Rating Scale (C-SSRS) training, a 30-minute interactive slide presentation followed by a question-answer session. The C-SSRS is a scale that can delineate high, moderate, and low-risk levels.

Suicidality Response Plan

The Suicidality Response Plan can be activated if the study team have in-person or telephone interactions that concern them, deeming the participant as 'high risk.' Additionally, 'high risk' participants are defined as those who reply to the PHQ-9's question #9 regarding suicidal ideation with any response indicating a frequency of such ideation measured in days other than 'never' PLUS responding 'yes' to a branching logic item that follows any such 'positive' response to item #9 that determines if the individual has an active suicidality plan.

Protocol Version: 5.1 Dated: 13 June 2022 Page 17 of 42

If the participant is deemed to be at high risk of active suicidality, the app system will send an alert email and/or text message in real time to the study manager, the study coordinator(s) and the PIs (no PHI included, only study ID).

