One of these study staff will then contact the participant. Contact is to occur as soon as possible (and definitely within 24 hours of learning of the event). Using the full C-SSRS, the trained staff will then help to assess the participant to determine if they endorse active suicidal ideation. The trained staff will also determine if the participant is currently being treated by a mental health professional.

If the participant is considered to be *actively suicidal* then at least one of the following plans will be followed depending on the location of the participant for each of the following situations:

Situation 1

- If the participant is with one of the study personnel, the study personnel will notify the PIs immediately.
- The study personnel will either physically walk the subject to the emergency department, or call a Psychiatric Emergency services number relevant to the site as described above.

Situation 2

- o If the participant is on the telephone:
 - The study personnel will notify the PIs immediately
 - The study personnel will stay on the telephone with the subject participant.
 - The study personnel will immediately contact 911 to initiate an on-site rescue if such action is clinically indicated.
- The study personnel will stay on the telephone with the subject until EMS services have contacted the participant.

Situation 3:

- If there are any active suicidal concerns in any of the surveys (e.g., PHQ-9 above), an email, or in a text message:
 - The study data system will notify the PIs and Study Manager in real time of any PHQ-9 suicidality item positively endorsed.
 - The study personnel will then contact the honest broker to de-identify the participant information.
 - Next, the study personnel (or a PI; whoever is able first) will contact the participant by telephone.
 - The study personnel or PI will stay on the telephone with the subject participant
 - The study personnel or PI will use a different telephone line to immediately contact 911 to initiate an on-site rescue if action is clinically indicated.
 - The study personnel or PI will stay on the telephone with the subject until EMS services have contacted the participant.

If the participant if determined to be actively suicidal and require immediate medical therapy, they will be withdrawn from the study.

If the family member is deemed not to be actively suicidal, they will be given a list of local mental health resources within the app platform's screen as follows:

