- 2. Moderate: minimal, local, or non-invasive intervention indicated; moderate impact on ADL. For example, suicidal ideation endorsed (i.e., PHQ-9 item #9), though no plan endorsed.
- 3. Severe: significant symptoms requiring invasive intervention; subject seeks medical attention, needs major assistance with ADL. For example, suicide attempt, hospitalization due to distress symptoms, or death.

Reporting Procedures

Adverse and Serious Adverse Events

We have a strong plan for AE/SAE reporting and follow up. First, we have a very robust monitoring system for psychiatric and emotional symptoms. We will know 'alert' values of depression, anxiety, and PTSD symptoms the second a questionnaire is completed via the mobile app. For symptoms that are either great in total burden (i.e., total score is high), we will call the participant to check in. For specific symptoms such as the suicidal ideation item in the PHQ-9 depression questionnaire, we will also call the participant and assess the severity of the situation, triaging them as appropriate to psychiatric support. Last, we have broadly placed our email addresses and phone numbers in all study materials and will encourage people to contact us regarding any issues.

Since this is a psychosocial intervention, we do not expect study related physical issues to occur. Furthermore, there is no lab work involved.

All deaths will be reported to NIA Program Officer, the DSMB Chair, and the central IRB within 72 hours of study's knowledge of death. For each patient who dies, a brief report containing the following variables will be provided:

Age
Principal diagnosis
Number of comorbidities
Admission APACHE II score
Days since enrollment

Protocol Version: 5.1 Dated: 13 June 2022 Page 21 of 42

Brief description of circumstances surrounding death including expected or unexpected.

All **adverse events that are both serious** (SAE) **and unexpected** (i.e., have not been previously reported for the study's intervention) will be reported to the IRB, NIA PO, and to the independent data and safety monitoring body according to the timeframe displayed in appendix 6. The summary of all other SAEs should be reported to NIA PO and to the DSMB or a Safety Officer, if either is appointed, quarterly, unless otherwise requested by the DSMB or a Safety Officer.

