Serious (fatal or life-threatening) SAEs that are unanticipated (i.e., not listed in the Data and Safety Monitoring Plan) and that are related to the intervention will be reported to the NIH Program Officer and to the DSMB Chair according to the timeframe displayed in appendix 6.

The summary of all other SAEs will be reported to NIH Program Officer and to the DSMB quarterly, unless otherwise requested by the DSMB. Additionally, for SAEs, we will hold an all-investigator

teleconference within 7 days. The PIs will draft a description of the SAE and an action plan. This will be passed on to the IRB, the NIH, and DSMB within 72 hours of the teleconference. See appendix 6 for identifying and reporting structure.

Protocol Deviations and Other Unanticipated Problem Reporting

Incidents or events that meet the reporting criteria, as outlined by the Duke IRB, will be reported to the Duke IRB as needed.

The following will be included, at a minimum:

Table	
Information	Timing
Study operations: Enrollment rate,	Reviewed on a weekly basis
refusals, dropouts	
Intervention adherence: Total app logins, number of pages viewed per use, surveys completed, total time	Numerous dimensions via software analytics
spent per login	
Distress:	
-Suicidal ideation	-Real-time monitoring with automated email alert sent to all study staff if suicidal ideation present
-Psychological distress symptoms	-Every 6 months by DSMB and every year by IRB
Unanticipated Problems, Adverse	Reviewed by PI and study staff
Events, and Serious Adverse	immediately on discovery.
Events: hospitalizations, life-	•
threatening events, death	

- A detailed description of the event, incident, experience, or outcome;
- A description of any changes to the protocol or other corrective actions that have been taken or are proposed in response to the unanticipated problem.

12. Data & Safety Monitoring Plan

Overall framework for safety monitoring and what information will be monitored

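### The protocol contradicts itself on whether a caregiver with suicidal ideation but no active plan triggers an alert, a call and an adverse event

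*Combined protocol and SAP*

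**What the plan says.** **Section 10, Suicidality Response Plan.** A survey makes a participant high risk when PHQ-9 item 9 is answered at any frequency other than never, "PLUS responding 'yes' to a branching logic item that follows any such 'positive' response to item #9". That follow-up item is the one "that determines if the individual has an active suicidality plan". The alert is attached to this status: "If the participant is deemed to be at high risk of active suicidality, the app system will send an alert email and/or text message". It goes to the study manager, the coordinator(s) and the PIs. Contact within 24 hours and a full C-SSRS assessment follow. Staff can also activate the plan if an in-person or telephone interaction concerns them.

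**Section 10, item (4) of the distress measures.** "For issues such as passive suicidal ideation or symptoms of depression, anxiety, or PTSD, an informational sheet will be provided", with contact numbers. No call is mentioned.

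**Section 10, Situation 3.** The data system notifies the PIs and Study Manager "in real time of any PHQ-9 suicidality item positively endorsed". This bullet sits under a lead-in about active suicidal concerns, within a block for participants considered actively suicidal.

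**Section 11, Reporting Procedures.** "For specific symptoms such as the suicidal ideation item in the PHQ-9 depression questionnaire, we will also call the participant" and assess how severe the situation is. No plan condition is attached.

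**Section 11, monitoring table.** Real-time monitoring, with an "automated email alert sent to all study staff if suicidal ideation present".

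**Section 12.** Overall framework and the later Safety Monitoring subsection both say staff are alerted at once to any report of suicidal ideation. Frequency of Data and Safety Monitoring says all study staff learn of it in real time.

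**AE definition.** Abbreviations and Definitions counts any suicidal ideation. Section 11 (Adverse Events and Serious Adverse Events) first requires the ideation item plus active planning, then restricts AEs to ideation with intent or thoughts of intent. Section 11 (Severity) gives ideation endorsed without a plan as its example of a moderate AE.

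**The concern.** The automated alert is the main safeguard here. Section 3 (Aim 2) says family members complete the surveys remotely and electronically, and Appendix 5 schedules the PHQ-9 at T1, T3 and T4. Often no staff member will be present when item 9 is answered, so what happens next depends on how the app's trigger is programmed.

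One group falls between the rules: caregivers who report ideation and answer no to the plan item. If the app follows the high-risk definition alone, these caregivers raise no alert, although sections 11 and 12 say staff will be alerted and section 11 says the caregiver will be called.

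Three further consequences follow. Section 12 names AE reports and the PHQ-9 ideation item as the primary safety measures, so an AE definition that shifts between sections affects what the DSMB is shown. Section 11 gives a late staff response to reported ideation as an example of an unanticipated problem, which cannot be judged while the required response is unclear. Section 10 says participants are told the response plan before they sign consent, so what they are told is uncertain too.

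**Working it through.** No sample size, power or event figure enters this point. The check is to take one caregiver (item 9 positive, plan item answered no) through every place that states a trigger, a response or an AE rule, and to compare with a caregiver who answers yes to the plan item.

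**Step 1: alert**

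| Place | Item 9 positive, no plan | Item 9 positive, plan | Recipients |
|---|---|---|---|
| Section 10, high-risk definition and alert | No alert provided for | Alert | Study manager, coordinator(s), PIs |
| Section 10, Situation 3 | Alert on the bullet's own words; unclear given its lead-in | Alert | PIs, Study Manager |
| Section 11, monitoring table | Alert | Alert | All study staff |
| Section 12, Overall framework | Alert | Alert | Study staff |
| Section 12, Frequency of Data and Safety Monitoring | Alert | Alert | All study staff |
| Section 12, Safety Monitoring | Alert | Alert | Study staff |

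With a plan, every place agrees that an alert is sent. Without one, the section 10 definition stands against four statements in sections 11 and 12, and Situation 3 can be read either way. The contradiction does not need Situation 3.

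**Step 2: response when there is no plan**

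- Section 10, item (4): an information sheet, no call mentioned.
- Section 11, Reporting Procedures: a call and an assessment of severity.
- Section 10, after Situation 3: an on-screen resource list for those judged not actively suicidal. This may come after a call and assessment, so it does not settle the matter.
- The 24-hour limit and the C-SSRS follow the high-risk alert. Whether they apply to this caregiver is not stated.

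**Step 3: adverse event when there is no plan**

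- Abbreviations and Definitions: an AE.
- Section 11, ideation plus planning: not an AE.
- Section 11, next paragraph: depends on intent rather than on a plan.
- Section 11, Severity: a moderate AE.

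If k caregivers report ideation with neither plan nor intent, they add k participants with an AE under the first and last rules, and 0 from this symptom under the two in between. The documents give no value for k.

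**The case against.** The best defence is that the text describes two tiers. Section 10 says an alert is sent if the participant is high risk; it does not say only then. An app could send a general notice to all staff on any positive item 9, and an urgent alert to a smaller group when a plan is also reported. The different recipient lists would fit. This is technically possible, so a reader should not infer that the system can implement only one of the rules. But no section states the tiers, and the Suicidality Response Plan describes a single app alert.

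Other stronger readings are also unsupported:

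- **That this caregiver would get a leaflet and nothing else.** Item (4) does not exclude a call, and a sheet plus a call would satisfy both item (4) and section 11. The accurate statement is that item (4) mentions no call while section 11 promises one.
- **That Situation 3 itself promises a call for any positive item 9.** Its telephone steps belong to the block on participants considered actively suicidal. Only Reporting Procedures in section 11 ties a call to the ideation item without a plan condition.
- **That about 7 of 150 caregivers are affected.** Section 10 reports that under 5% of participants in earlier similar studies needed a call, and 5% of 150 is 7.5. The text does not say what triggered those calls, and the surrounding paragraphs also cover severe distress without suicidality. If the calls followed the item-plus-plan rule, the disputed group lies outside that 5%.
- **That the item 9 data seen by the DSMB will fail to match the contact log.** These are separate records, and no section requires them to agree.

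Staff concern can also activate the plan, but that route needs in-person or telephone contact, which a remote survey does not supply.

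**Conclusion.** The point stands as an internal contradiction, limited to caregivers who endorse item 9 and report no active plan. For them the section 10 trigger provides for no alert, while the section 11 table and three subsections of section 12 say staff are alerted. Item (4) and Reporting Procedures describe different responses, the recipient lists differ, and the AE rules disagree. Caregivers who also report a plan trigger an alert under every version.

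The number affected cannot be derived, because the documents give no rate of item 9 endorsement with or without a plan. The missed alert is conditional on the app being built to the section 10 definition alone; the documents do not show how it is programmed. The point should be corrected because it concerns the main participant-safety mechanism and the correction is cheap.

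**What to change.** Reconcile these places into one stated trigger, or explicitly stated tiers, with one recipient list and one response for each level:

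- the AE entry in Abbreviations and Definitions;
- section 10: item (4), the Suicidality Response Plan and Situation 3;
- section 11: the AE/SAE definition, Severity, Reporting Procedures and the monitoring table;
- section 12: Overall framework, Frequency of Data and Safety Monitoring, and Safety Monitoring, including the repeated frequency-of-monitoring text that follows it.

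State whether the 24-hour contact limit and the C-SSRS apply at each level. Align the AE definition so that counts do not depend on which section staff follow. Then verify the app's alert logic against the agreed text with test responses covering item 9 negative, item 9 positive without a plan, and item 9 positive with a plan. Check that what participants are told at consent matches.

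Which trigger and which response are right is a clinical decision for the investigators and the DSMB.

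Cost: a protocol clarification and an app logic check. Sample size and the efficacy analysis are untouched.
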